8.3.3 Primary Efficacy Analyses

The FACE-Q™: Satisfaction with Facial Appearance questionnaire will be given at the Screening visit and the final study visit (V7). Change from baseline in the overall Rasch-transformed score to the final study visit will be summarized descriptively by treatment group and overall and will be analyzed using a one-sample t-test (or Wilcoxon signed-rank test if the normality assumption is not met) for the Evaluable Population. See SPP Appendix C for the calculation of the overall Rasch-transformed score.

The number and percentage of subjects who provide responses to the FACE-Q™ Satisfaction with Facial Appearance questionnaire will also be summarized descriptively by treatment group and overall based on the following categories for each FACE-Q™ question:

- 1. Very Dissatisfied
- 2. Somewhat Dissatisfied
- 3. Somewhat Satisfied
- 4. Very Satisfied

A listing for FACE-Q™ Satisfaction with Facial Appearance will be provided for the Safety Population.

8.3.4 Additional Analyses of the Primary Efficacy Endpoints

Not applicable.

8.4 Secondary Efficacy Endpoints and Analyses

8.4.1 Secondary Efficacy Endpoints

The key secondary efficacy endpoints are:

- Subject's assessment of aging appraisal as measured by the change from baseline in the Rasch-transformed score of the FACE-Q™: Aging Appraisal to final study visit (V7)
- Subject's assessment of psychological function as measured by the change from baseline in the Rasch-transformed score of the FACE-Q™: Psychological Function Scale to final study visit (V7)

- Subject's assessment of social function as measured by the change from baseline in the Rasch-transformed score of the FACE-Q™: Social Function Scale to final study visit (V7)
- Subject's assessment of satisfaction with skin as measured by the change from baseline in the Rasch-transformed score of the FACE-Q™: Satisfaction with Skin to final study visit (V7)
- Subject's assessment of age-related facial appearance by the Self-Perception of Age (SPA) measure at baseline to final study visit (V7); responders are defined as having achieved a younger category.

Other secondary efficacy endpoints are:

- Investigator's assessment of global facial aesthetic improvement as measured by the 5-point GAIS at final study visit (V7)
- Subject's assessment of global facial aesthetic improvement as measured by the 5-point GAIS at final study visit (V7)
- Change in subject's satisfaction with appearance of periorbital area as measured by the change from baseline in the Periorbital Aesthetic Appearance Questionnaire (PAAQ) to final study visit (V7)

8.4.2 Secondary Efficacy Analyses

Change from baseline in the Rasch-transformed score of FACE-Q™ questionnaires (FACE-Q™: Aging Appraisal, FACE-Q™: Psychological Function, FACE-Q™: Social Function, FACE-Q™: Satisfaction with Skin) will be summarized descriptively by treatment group, gender, and overall and will be analyzed using a one sample t-test (or Wilcoxon signed-rank test if normality assumptions are not met) for the Evaluable Population. See SPP Appendix D, Appendix E, Appendix F, and Appendix G for the calculation of the overall Rasch-transformed score for each FACE-Q™ questionnaire.

The number and percentage of subjects who provide responses to each FACE-Q™ questionnaire will also be summarized descriptively by treatment group, gender, and overall, for the Evaluable Population, based on the following categories for each questionnaire:

- FACE-Q™ Aging Appraisal
 - 1. Definitely Agree
 - 2. Somewhat Agree
 - 3. Somewhat Disagree
 - 4. Definitely Disagree
- FACE-Q™ Psychological Function, FACE-Q™ Social Function
 - 1. Definitely Disagree
 - 2. Somewhat Disagree
 - 3. Somewhat Agree
 - 4. Definitely Agree
- FACE-Q™ Satisfaction with Skin
 - 1. Very Dissatisfied
 - 2. Somewhat Dissatisfied
 - 3. Somewhat Satisfied
 - 4. Very Satisfied

For the Self-Perception of Age (SPA) questionnaire, the number and percentage of subjects who look their current age will be summarized for baseline and the final study visit by treatment group, gender, and overall, for the Evaluable Population. The change from baseline in the number of years look younger and older to the final study visit will be summarized descriptively by treatment group, gender, and overall, for the Evaluable Population.

A shift table to summarize the changes into an improvement category from the baseline to the final study visit will be provided in frequency and percentage. No statistical testing for the shift table will be performed.

There are two assessment categories in GAIS at the final study visit: subject rating and investigator rating. Descriptive summaries will be provided in frequency and percentage of the scales at the final study visit, in the 5-point scale from -2 to +2 by treatment group, gender, and overall, for the Evaluable Population. The scales include:

- 2: Much Improved
- 1: Improved
- 0: No Change
- -1: Worse
- -2: Much Worse

Descriptive summaries will be provided in frequency and percentage for nine questions of PAAQ at baseline and the final study visit by treatment group, gender, and overall, for the Evaluable Population, with five categories of answers for each question. Five categories of answer include:

- 0. Never
- 1. Rarely
- 2. Some of the Time
- 3. Most of the Time
- 4. All of the Time

The PAAQ will also be summarized in the transformed total score and three domains, using descriptive statistics by treatment group, gender, and overall and will be analyzed using a one-sample t-test (or Wilcoxon signed-rank test if normality assumption is not met) for the Evaluable Population.

The transformed scale score is calculated as $[(\text{actual raw score} - \text{lowest possible raw score}) / \text{possible raw score range}] * 100$. This formula can be simplified as $[(\text{actual raw score} - 0) / 4] * 100$.

The transformed total score is calculated as [(actual total raw score - lowest possible total raw score) / (possible total raw score range)] * 100. This formula can be simplified as [(actual total raw score - 0) / 36] *100.

Three domains include psychological domain, appearance domain, and coping domain. The psychological domain is defined as (sum of transformed scale score in PAAQ questions of 2, 4, 6, 7, and 8) / (number of questions). This formula can be simplified as (sum of transformed scale score in PAAQ questions of 2, 4, 6, 7 and 8) / 5.

Similar manner will be applied to the appearance domain and the coping domain, but with different number of PAAQ questions included for each domain. The appearance domain includes PAAQ questions of 1, 3 and 5. The coping domain contains only PAAQ question 9. See SPP Appendix H for the details of domain score calculation and missing data imputation.

Listings will be provided for FACE-Q™: Aging Appraisal, FACE-Q™: Psychological Function, FACE-Q™: Social Function, FACE-Q™: Satisfaction with Skin, SPA, GAIS, and PAAQ for the Safety Population.

A figure will be provided for the change from baseline of each FACE-Q™ questionnaires (Satisfaction with Facial Appearance, Aging Appraisal, Psychological Function, Social Function, and Satisfaction with Skin) in the Rasch-transformed score by treatment group and gender, for the Evaluable Population.

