1.0 Introduction

This Statistical Analysis Plan (SAP), based on Protocol Amendment 1 Version 2, 18-Oct-2021, describes the statistical analyses for AbbVie Study CMA-MA-FAS-0580 HARMONY Brazil: Prospective, Multi-site, Study to Evaluate Subject Satisfaction with Facial Appearance Overall and the Aesthetic and Psychosocial Impact of Combined Facial Treatment. Specifications of tables, figures, and data listings are contained in a separate document.

Study CMA-MA-FAS-0580 is a prospective, interventional, multicenter, combination filler medical device and drug post marketing study. Approximately 60 subjects will be enrolled consecutively at approximately 7 study sites in Brazil. Recruitment will also target men, who are typically under-represented in aesthetic studies. Each subject will be in the study for up to approximately 5 months and act as his/her own control. Subjects will be evaluated by the investigator to receive BOTOX, HArmonyCa Lidocaine facial filler, and Juvéderm facial fillers (JUVÉDERM VOLITE [REDACTED], JUVÉDERM VOLBELLA with Lidocaine, JUVÉDERM VOLIFT with Lidocaine, JUVÉDERM VOLUMA with Lidocaine, and JUVÉDERM VOLUX with Lidocaine). Selected subjects will receive staged treatment with the multiple products and will be evaluated using validated patient-reported outcome measurements to determine the psychological and emotional impact of an integrated treatment approach to reduce visible signs of aging. All products will be used as per their license only.

The SAP will not be updated in case of administrative changes or amendments to the protocol unless the changes impact the analysis.

Unless noted otherwise, all analyses will be performed using SAS Version 9.4 (SAS Institute Inc., Cary, NC 27513) or later.

This SAP includes changes to analyses described in the protocol. Details are outlined in [Appendix C](#).

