8.0 Efficacy Analyses

8.1 General Considerations

- All efficacy analyses will be conducted in the Evaluable Population.
- Day 1 is defined as the day on which the study treatment is first received.
- Baseline for efficacy is defined as the last non-missing assessment on or prior to Day 1.
- Study day is relative to Day 1.
- Change from baseline will be computed as post-baseline minus baseline.

- Categorical variables will be summarized descriptively using number of subjects with observed values or events (n) and the percentage of subjects with observed values or events.
- Continuous variables will be summarized descriptively using number of subjects with observed values (n), mean, standard deviation (SD), standard error of mean (SEM), median, minimum (min), and maximum (max).
- Unless otherwise specified, the estimated mean and median for a set of values will be printed out to 1 more significant digit than the original values; the SD and SEM will be printed out to 2 more significant digits than the original values; the min and max will report the same significant digits as the original values.
- Shapiro-Wilks test will be used to check the normality assumption. If the normality assumption is met, the statistical hypothesis test will be performed based on one-sample, one-sided t-test at 0.025 significance level. If the normality assumption is not met, Wilcoxon signed-rank test will be used instead and a 97.5% confidence interval (CI) for the median will be presented using the Hodges Lehmann method. Shapiro-Wilks and Wilcoxon signed-rank test will be performed by proc univariate procedure, and Hodges Lehmann CI of the median for paired samples will be performed based on a SAS macro by Han (2008) [\[1\]](#) as specified in SPP Section 3.3.
- All CIs will be 1-sided 97.5% CIs, and will be printed to 2 decimal places, unless stated otherwise. P-values output will be in the format: ‘0.xxxx’, where xxxx is the value rounded to 4 decimal places. Every p-value less than 0.0001 will be presented as <0.0001. If the p-value is returned as >0.9999, then present it as it is.
- Unless otherwise specified, the summaries will be provided by treatment group, gender, and overall.

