8.2 Handling of Missing Data

For all FACE-Q™ questionnaires, the sum of the items will be calculated and converted into an overall score (also known as the Rasch-transformed score) ranging from 0 (worst) to 100 (best). If the number of missing items (which includes selection of more than 1 response for an item, a response of non-applicable (N/A) or skipping a question) is at most 50% of all the items, then insert the unrounded mean of the completed items into the total sum score. Inversely, if the

number of missing items is more than 50%, then the overall score will be missing. The total score will not be calculated in this case and the particular visit will be excluded from the Rasch-transformed score calculation and summary.

For PAAQ questionnaire, all items will be transformed to a scale from 0 (no negative impact) to 100 (high negative impact). Domain scores will be calculated as the average of transformed scale scores using the 50% rule given below:

If the domain has at least 50% non-missing item responses it will be scored as the average of the non-missing responses (with reverse scoring and rescaling as appropriate). If the domain is missing more than 50% of item responses, then the domain score will be set to missing.

For all other questionnaires as specified below, no imputation will be performed.

- Self-Perception of Age Questionnaire
- Global Aesthetic Improvement Scale

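### Does the planned summary of change in self-perceived age (years looking younger or older) drop every responder?

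*SAP*

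**What the plan says.** SPA is a key secondary endpoint, assessed at screening and at the final visit (V7). SAP 3.2.1 and 8.4.1 define it by category: "responders are defined as having achieved a younger category". SAP 8.4.2 plans three outputs, each for the Evaluable Population or within its efficacy analyses:

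- At each visit, "the number and percentage of subjects who look their current age will be summarized for baseline and the final study visit".
- "The change from baseline in the number of years look younger and older to the final study visit will be summarized descriptively".
- "A shift table to summarize the changes into an improvement category from the baseline to the final study visit will be provided", as frequency and percentage and without a test.

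Three general rules bear on the second output. SAP 8.1 states "Change from baseline will be computed as post-baseline minus baseline", and it bases continuous summaries on observed values and reports their n. SAP 8.2 states "For all other questionnaires as specified below, no imputation will be performed", and the list that follows names SPA.

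SAP 1.0 adds: "Specifications of tables, figures, and data listings are contained in a separate document". The SPA form is Protocol Appendix 1, whose content is not in the text available for review.

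**The concern.** SAP 8.4.2 implies three kinds of SPA answer: looks current age, looks some years younger, looks some years older. On those three states every responder changes state. Suppose years younger and years older are separate variables, each filled only when it applies. A subject who moves from older to current age then has years older at baseline and nothing to subtract it from at V7. A subject who moves from current age to younger has years younger at V7 and no baseline value. Read together, the change rule, the observed-values rule and the no-imputation rule seem to remove both.

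On that reading, the only numeric SPA summary would describe only subjects who stayed older or stayed younger, and the most subjects it could contain would fall as the response rate rose. The percentage looking their current age would not compensate, because moves into and out of that state can cancel. For a key secondary endpoint, the table could then show little change in a study where many subjects improved.

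**Working it through.** **Inputs.** The documents give no figure for SPA years. The one plan figure used is the evaluable sample size of 48 (SAP 2.4). It reproduces: a one-sample, one-sided t-test at 0.025 with mean 12.0 and SD 25.0 has power 0.9027 at n = 48 and 0.8964 at n = 47, and 48 / (1 - 0.20) = 60 enrolled. The three-category scale and all years below are assumptions.

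**Responder moves under three codings.** Let *a* be years older at baseline and *b* years younger at V7. Change is V7 minus baseline. The signed variable takes older as positive, current age as 0 and younger as negative.

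| Move | Two counts, blanks | Two counts, zeros (older; younger) | One signed variable |
|---|---|---|---|
| older to current | neither defined | -a; 0 | -a |
| older to younger | neither defined | -a; +b | -a - b |
| current to younger | neither defined | 0; +b | -b |

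Defined responder moves: 0 of 3 with blanks, 3 of 3 with zeros, 3 of 3 with the signed variable. With blanks, only subjects who stay older or stay younger have a change. With zeros, change in years older minus change in years younger equals the signed change in every row, so the two means recombine exactly.

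**Illustration, N = 48 with 24 responders.** There are six groups of 8: older 5 to current; older 5 to younger 3; current to younger 3; older 5 to older 4; current to current; younger 3 to younger 4.

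- Blanks: n = 8 for years older (mean -1.0) and n = 8 for years younger (mean +1.0), with no responder in either.
- Zeros: years older 8 × (-5 - 5 - 1) / 48 = -1.83; years younger 8 × (3 + 3 + 1) / 48 = +1.17.
- Signed: 8 × (-5 - 8 - 3 - 1 + 0 - 1) / 48 = -3.00, which equals -1.83 - 1.17.
- Looks current age: 16/48 = 33.3% at both visits.

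The arithmetic of the concern is therefore right under blanks. The contrast comes from the coding, and its size comes from the assumed years and group sizes.

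**Does the SAP impose the blank coding?** It takes three steps to get there, and the text supplies none of them.

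1. *Two variables.* The sentence in 8.4.2 names a single change in years younger and older. One signed variable fits it as well as two counts do.
2. *Blanks.* The no-imputation line sits under the missing-data heading and concerns unanswered questionnaires. A subject who reports looking their current age has answered, and 0 years follows from that answer. The SAP neither requires nor forbids the zero.
3. *Three responder categories.* The endpoint refers to a younger category without listing the categories. If they were bands of years, a subject could respond while remaining older at both visits and would have a change even under blanks.

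**The case for a change.** The strongest case for a change is that the SAP is silent on any reading. A signed variable also needs a direction and a value for current age, and neither is given. For FACE-Q and PAAQ the SAP gives scoring text and points to appendices of the Statistical Programming Plan; for SPA it does neither. Zero-filled counts keep responders but split an older-to-younger move over two rows, and their SDs (2.29 and 1.36 in the illustration) do not give the signed SD of 2.80. The shift table refers to an improvement category where the endpoint refers to a younger category. Settling all this would take two sentences.

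What stands is that the derivation is not written in the SAP and that one possible coding would work badly. That falls short of a plan that drops responders. The table specifications are held in a separate document and the SPA form is not shown, so silence in the SAP body does not show how the variable will be programmed. The bad coding would also be visible: n is printed with the summary, so 8 and 8 out of 48 would stand out, and SPA listings are planned against which it could be checked. The difference between the two category terms is one of wording; in context both describe a move towards looking younger.

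**Conclusion.** No change to the plan follows. SAP 8.4.2 leaves the SPA years variable undefined, but the loss of every responder depends on coding choices the SAP does not make: 0 of 3 responder moves are defined under two counts with blanks, and 3 of 3 under either natural alternative. A programmer faced with a subject who answered that they look their current age can be expected to record 0 years.

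Little is at stake. The endpoint is category response, which does not use the years variable, and the shift table gives its count and percentage. The years summary is descriptive and untested, in a single-arm study, and neither the sample size nor any test depends on it. This conclusion assumes that the table specifications, which were not available, handle a current-age answer as an observed value. If they instead used blanks, the effect would be confined to this one summary.

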8.5 Subgroup Analyses

A subgroup analysis on the primary efficacy endpoints (change from baseline in the overall Rasch-transformed score of the FACE-Q™: Satisfaction with Facial Appearance Scale to the final study visit) will be performed by gender and overall.

9.0 Safety Analyses

9.1 General Considerations

- All safety analyses will be conducted by treatment group, gender, and overall, for the Safety Population.

- Adverse events (AEs) will be coded using the medical dictionary for Regulatory Activities (MedDRA). The actual version of the MedDRA coding dictionary will be noted in the statistical outputs and clinical study report.

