### 5.1 Inclusion Criteria

The following are requirements for entry into the study.

1. 35 to 65 years of age, inclusive, at screening (male or female)
2. Accept the obligation not to receive any other facial procedures or treatments at any time during the study that are not related to the study
3. Women of childbearing potential must have a negative urine pregnancy test before each injectable treatment and practice a reliable method of contraception throughout the study
4. Willing to avoid direct and prolonged sun exposure to the facial skin, which includes tanning beds, for the duration of the study
5. Must qualify to receive BOTOX treatments, in at least one area, as per the approved Product Monograph including treatment of hyperkinetic lines for the glabellar, crow's feet, and forehead lines:
  - Glabellar injection: glabellar rhytides characterized as 2 (moderate) or 3 (severe) during maximum muscle contraction on the evaluation of the facial wrinkle scale (FWS)
  - CFLs characterized as 2 (moderate) or 3 (severe) during maximum smile on the evaluation of the FWS
  - FHLs of 2 (moderate) to 3 (severe) rating at maximum eyebrow elevation as assessed using the FWS
6. Must qualify to receive Juvéderm dermal filler treatments as per the approved Directions for Use. Subjects must use at least two different Juvéderm filler products in at least two different aesthetic anatomic areas. A summary of inclusion criteria by facial area for potential subjects for filler treatments is presented in [Table 5.1](#).

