### 6.2.3 Visit V3 and V4 (Juvéderm)

V3 will occur  $30 \pm 7$  days after previous treatment. If HArmonyCa is not given to the subject, the subject may begin with Juvéderm filler injections and V3 activities as outlined in this section and in Table 6.1. If no HArmonyCa is administered, please see guidance regarding screening and first treatment occurring on the same day outlined in Section 6.2.2. V3 and V4 are mandatory regardless of whether further filler treatment is expected. The following study procedures and treatments will be performed at V3 and V4:

- Record concomitant medications.
- Perform urine pregnancy test for women of childbearing potential.
- Record AEs.
- Dispense subject diary to record AEs; counsel subject on diary entries that are needed during the next 30 days
- Perform facial Juvéderm filler injections.

- Facial filler injections (JUVÉDERM VOLBELLA with Lidocaine, and/or JUVÉDERM VOLIFT with Lidocaine, and/or JUVÉDERM VOLUMA with Lidocaine, and/or JUVÉDERM VOLITE [REDACTED] and/or JUVÉDERM VOLUX with Lidocaine) will be administered into areas that the subject desires and qualified for per the inclusion/exclusion criteria and within the approved clinical indications (Section 5.1 and Section 5.2, respectively).

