2.2 Study Design Overview

This Phase 4 study is a prospective, interventional, multicenter, combination medical device and drug post marketing study. Each subject will be in the study for up to approximately 5 months and act as his/her own control. All products will be used as per their license only. The investigators will perform all treatments and evaluations.

The study is planned to enroll 60 subjects consecutively at approximately 7 study sites in Brazil. Recruitment will also target men, who are typically under-represented in aesthetic studies.

All subjects will sign an informed consent form (ICF) and begin the study at the screening visit (V0). Subjects following screening (V0) will enter the study and receive an initial treatment of HArmonyCa Lidocaine at Visit 1 (V1), followed by Juvéderm fillers at Visit 3 (V3), and BOTOX at Visit 5 (V5) as indicated in the study design diagram ([Figure 1](#)). If the decision is made to not treat with HArmonyCa Lidocaine, the subject may begin with Juvéderm fillers at V1. As indicated in the diagram, touch-ups of HArmonyCa at Visit 2 (V2), Juvéderm at Visit 5 (V5), and BOTOX at Visit 6 (V6) are optional. If a touch-up of HArmonyCa (V2) is not performed, the subject may advance in the study timeline to the next study visit procedures. If a touch-up of BOTOX is not performed, the subject will return on schedule for Visit 7 (V7). A

subject not receiving Juvéderm touch-up would continue with BOTOX treatment (and all study procedures) outlined for V5. To reduce the number of subject visits, V0 can be combined with the initial treatment visit (V1), if judged by the investigator to be appropriate and acceptable for the subject. End of study is the last clinical visit an enrolled subject has in this study, V7 (after approximately 5 months of treatment). Subjects who discontinue prematurely will be asked to return for the last clinical visit for end-of-study data collection. Identical study procedures will not be repeated where the visits are combined. The schedule of activities is shown in [Table 1](#).

Figure 1. Study Design

[figure not shown]

Table 2. Schedule of Activities (SOA)

Study Visit	V0 ¹	V1	V2	V3	V4	V5	V6 ²	V7 ³
Visit window	Screening	Day 1	Day 30	Day 60	Day 90	Day 120	Day 135	Day 150
	(Day -14 to Day -1)	N/A	(30 ± 7 days after V1)	(30 ± 7 days after V2)	(30 ± 7 days after V3)	(30 ± 7 days after V4)	(15 ± 7 days after V5)	(15 ± 7 days after V6)
STUDY TREATMENTS								

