2.3 Treatment Assignment and Blinding

Approximately 60 subjects will be enrolled consecutively at approximately 7 study sites in Brazil. Recruitment will also target men, who are typically under-represented in aesthetic studies. Study treatments include:

- **BOTOX:** The dose and the number of injection points may be adapted to the needs of the subject, based on their characteristics and location of the muscles to be treated. Subjects will receive at least one BOTOX treatment in the following areas: glabellar lines (GLs), crow's feet lines (CFLs), and forehead lines (FHLs).
- **HArmonyCa Lidocaine:** The investigator will determine the appropriate volume to be injected during initial and touch-up treatments based on his/her clinical experience. The maximum total volume of HArmonyCa Lidocaine allowed per subject for the initial and touch-up treatment combined is 4 syringes (5 milliliter [mL]).
- **JUVÉDERM:** The investigator will determine the appropriate volume to be injected during initial and touch-up treatments based on his/her clinical experience.
 - JUVÉDERM VOLITE [REDACTED]: The maximum total volume of JUVÉDERM VOLITE [REDACTED] allowed per subject for the initial and touch-up treatments combined is 4 syringes (4 mL).
 - JUVÉDERM VOLBELLA with Lidocaine: The maximum combined total volume of JUVÉDERM VOLBELLA with Lidocaine allowed per subject for all facial areas treated for both the initial and touch-up treatments combined is 2 syringes (2 mL).
 - JUVÉDERM VOLIFT with Lidocaine: The maximum total volume of JUVÉDERM VOLIFT with Lidocaine allowed per subject for the initial and touch-up treatments combined is 4 syringes (4 mL).
 - JUVÉDERM VOLUMA with Lidocaine: The maximum total volume of JUVÉDERM VOLUMA with Lidocaine allowed per subject for the initial and touch-up treatments combined is 4 syringes (4 mL).

- JUVÉDERM VOLUX with Lidocaine: The maximum total volume of JUVÉDERM VOLUX with Lidocaine allowed per subject for the initial and touch-up treatments combined is 4 syringes (4 mL).

The investigator should not inject greater than 20 mL of filler (Juvéderm and HArmonyCa Lidocaine) per 60 kg (130 lbs.) body mass per year for a single subject.

Blinding and randomization are not applicable. This is an open-label, single-arm study. Subjects are enrolled consecutively based upon subject need and all subjects are intended to receive all treatments. Investigators will perform all treatments and evaluations.

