4.1.3 Safety Population

The Safety Population is defined as all subjects who received any product as treatment in this study.

Unless otherwise specified, all efficacy analyses will be based on the Evaluable Population. The mITT Population will be used for demographics and baseline characteristics summary. The Safety Population will be used for the protocol deviation and violation, treatment exposure, all safety analyses, and listings unless otherwise specified.

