9.2.2 Adverse Event Overview

Overall summaries of TEAEs will include:

- The number and percentage of subjects with any TEAE
- The number and percentage of subjects with any TESAE
- The number and percentage of subjects with any severe TEAE
- The number and percentage of subjects with any TEAE related to JUVÉDERM VOLITE
- The number and percentage of subjects with any TEAE related to JUVÉDERM VOLBELLA
- The number and percentage of subjects with any TEAE related to JUVÉDERM VOLIFT
- The number and percentage of subjects with any TEAE related to JUVÉDERM VOLUMA
- The number and percentage of subjects with any TEAE related to JUVÉDERM VOLUX
- The number and percentage of subjects with any TEAE related to BOTOX cosmetic
- The number and percentage of subjects with any TEAE related to study procedure
- The number and percentage of subjects with any TEAE related to device
- The number and percentage of subjects with any TEAE leading to study discontinuation

- The number and percentage of subjects with any TEAE leading to death
- The number and percentage of subjects with any TESAE related to JUVÉDERM VOLITE
- The number and percentage of subjects with any TESAE related to JUVÉDERM VOLBELLA
- The number and percentage of subjects with any TESAE related to JUVÉDERM VOLIFT
- The number and percentage of subjects with any TESAE related to JUVÉDERM VOLUMA
- The number and percentage of subjects with any TESAE related to JUVÉDERM VOLUX
- The number and percentage of subjects with any TESAE related to BOTOX cosmetic
- The number and percentage of subjects with any TESAE related to study procedure
- The number and percentage of subjects with any TESAE related to device
- The number and percentage of subjects with any TESAE leading to study discontinuation
- The number and percentage of subjects with any TESAE leading to death
 - Before BOTOX Treatment
 - On or After BOTOX Treatment

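### Product-specific related-TEAE and TESAE percentages are taken over everyone who received any product, which understates the rate for any product not given to all subjects

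*SAP*

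**What the plan says.** SAP 9.1 sets one rule for safety: "All safety analyses will be conducted by treatment group, gender, and overall, for the Safety Population". SAP 4.1.3 defines the set: "The Safety Population is defined as all subjects who received any product as treatment in this study". The treatment groups are HArmonyCA and Non-HArmonyCA (SAP 5.0), so the columns do not separate subjects by Juvéderm product or by BOTOX.

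Within that frame, the Adverse Event Overview (SAP 9.2.2) lists one row per product, from "The number and percentage of subjects with any TEAE related to JUVÉDERM VOLITE" to "The number and percentage of subjects with any TEAE related to JUVÉDERM VOLUX", then BOTOX, and repeats the list for TESAEs. The SOC/PT sections that follow name the same six products. None of these sections states a product-specific denominator.

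On exposure, Protocol 5.1 says: "Subjects must use at least two different Juvéderm filler products in at least two different aesthetic anatomic areas". Protocol 6.2.3 joins the five fillers by and/or, and they "will be administered into areas that the subject desires and qualified for per the inclusion/exclusion criteria". Protocol Table 5.1 limits VOLUX to the chin and mandible. Protocol Table 6.1 schedules the first BOTOX treatment at V5. HArmonyCa can be omitted: "If the decision is made to not treat with HArmonyCa Lidocaine, the subject may begin with Juvéderm fillers at V1". Pointing the other way, SAP 2.3 (like Protocol 4.4) says "all subjects are intended to receive all treatments".

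**The concern.** A subject who never received a given filler still counts in that filler's denominator. A row naming one product invites the reader to take its percentage as that product's event rate. As specified, it is that rate diluted by the share of the Safety Population that received the product. A seldom-used filler would look safer than a widely used one with the same rate among recipients.

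The planned summary tables may not let a reader undo this. SAP 6.0 names the number of injections and total and average volumes for each filler, but no count of subjects exposed. At stake is the product-level safety description. The primary efficacy analysis is not affected.

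**Working it through.** **1. The plan's own figure.** The documents give no figure for product-specific event rates. The only number needed from them is the planned size, 60 (Protocol 11.7, SAP 2.4). With a one-sample t-test, one-sided 0.025, mean change 12.0 and SD 25.0, power is 0.896 at n = 47 and 0.903 at n = 48. Then 48 / (1 − 0.20) = 60, so the figure reproduces. It serves here only as the size of the Safety Population if every enrolled subject is treated.

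**2. Formula.** Let N be the Safety Population, m the subjects who received the product, and x the exposed subjects with a related event.

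- Percentage as specified: 100·x/N
- Percentage among exposed: 100·x/m
- Understatement factor: (x/m) / (x/N) = N/m

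This assumes that the numerator holds exposed subjects only (see step 7).

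**3. Size over a range of exposure.** Exposure per filler and the event rate are assumptions. The rate among exposed is set at 20%.

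| Exposed m of 60 | Expected x | % over 60 | % over m | Factor |
|---|---|---|---|---|
| 60 | 12.0 | 20.0 | 20.0 | 1.0 |
| 48 | 9.6 | 16.0 | 20.0 | 1.25 |
| 36 | 7.2 | 12.0 | 20.0 | 1.67 |
| 24 | 4.8 | 8.0 | 20.0 | 2.5 |
| 12 | 2.4 | 4.0 | 20.0 | 5.0 |

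The factor does not depend on the assumed rate.

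**4. Link to the two-filler minimum.** If every subject receives exactly two fillers, there are 60 × 2 = 120 subject-filler exposures, or 120 / 5 = 24 per filler on average, and 60 / 24 = 2.5. With three, four or five fillers per subject, the average is 36, 48 or 60 and the ratio is 1.67, 1.25 or 1.0. These are ratios at average exposure. Individual fillers can lie on either side.

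**5. Comparability.** Take two fillers that both have a 20% rate, one used in 48 subjects and one in 12. The table would show 16.0% and 4.0%, a fourfold difference that comes from usage alone.

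**6. BOTOX.** All subjects are planned to receive it, so only those who leave before V5 dilute its row. If the whole 20% allowance left before V5, 48 of 60 would be exposed and the factor would be 1.25. That allowance also covers subjects who merely fail to complete the questionnaire at the end of study. On the plan's own assumption, 1.25 is therefore an upper figure.

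**7. Numerator.** SAP 9.2 imputes a causal relationship when it is missing for an AE on or after first study treatment. It does not limit this to products the subject received. An unexposed subject could therefore enter a product's numerator, which works against the dilution and is itself an error in that row.

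**8. Zero events, as illustration.** The SAP plans no confidence intervals for safety. At its one-sided 97.5% level (SAP 8.1), the upper bound with no events is 1 − 0.025^(1/m): 6.0% for m = 60, 7.4% for 48, 14.2% for 24 and 26.5% for 12. A zero read against 60 subjects would look more reassuring than the exposed number allows.

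**The case against.** Several points on the other side are fair.

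- **Exposure may be complete.** A reader might infer that every subject receives only some of the fillers, so that every filler is understated. The documents do not say this. Two is a minimum, all five are allowed, and both documents state an intention that all subjects receive all treatments. A filler given to everyone is not understated. That intention, however, is not worded per filler and sits beside the two-product minimum and the and/or wording, so it does not secure full exposure to all five.
- **The denominator is inferred.** SAP 9.2.2 writes none, and SAP 1.0 places the table specifications in a separate document that could set one. It is also unclear whether the related-event SOC/PT tables are per product or pooled. Still, the SAP's stated rule has no exception for product rows.
- **Exposed counts may be recoverable.** Protocol 11.3 plans exposure summaries by product and by combination, and SAP 6.0 lists all exposure data. This lets a determined reader rebuild the denominator from listings. It does not correct the percentage in the table.
- **The quantity is legitimate if labelled.** The share of all treated subjects with an event attributed to product X is a valid description of the regimen, and no between-product comparison is planned. This stands for any-TEAE and pooled rows. A row that names a single product and prints no exposed n is easily misread.

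**Conclusion.** The point holds for any product not given to every subject in the Safety Population: its related-TEAE and TESAE percentages are understated by N Safety / n exposed, and rows for differently used products are not comparable. This rests on reading SAP 9.1 and 4.1.3 as setting the denominator, and on numerators that contain exposed subjects only.

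The direction is certain under those conditions, but the size is not known. The factor is 1.0 if all 60 receive the filler, 1.25 if 48 do and 2.5 if 24 do. A reader might take 2.5 as the expected bias. It is only the ratio at average exposure if every subject receives exactly the minimum, and the documents give no exposure per filler. Nor does the 2.5 apply to BOTOX, where the effect is limited to subjects who leave before V5. The point covers the five Juvéderm fillers and BOTOX; the overview list has no HArmonyCa-related row, which is a separate matter.

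The correction should be made, because product-level safety reporting is affected. The study's main efficacy conclusion is not.

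**What to change.** In SAP 9.1, the Adverse Event Overview (9.2.2) and any product-specific SOC/PT table:

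- Use as denominator for each product's related TEAEs and TESAEs the subjects who received at least one injection of that product, and print that n in the row.
- Limit the numerator to the same subjects, with onset on or after their first injection of that product.
- In SAP 9.2, limit the imputation of missing causality to products the subject had received.
- Keep the full Safety Population for any-TEAE and pooled rows.

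Changing the denominator alone would not be enough, because imputed relationships could leave unexposed subjects in the numerator.

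The cost is SAP wording and a per-product exposure flag, with first-injection date, derived from injection data already collected. The downside is smaller denominators and somewhat less favourable percentages.
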